Numerous studies exist speaking to the efficacy of automated reminder (i.e. notifying parents of needed immunizations) and recall (i.e. notifying parents of overdue immunizations) systems, including text messaging systems.^{1,2,3} Other studies show that the combination of texting and calls proves even more successful in reaching patients.³ These systems are more cost effective and efficient. Differences in the timing of reminders to schedule, as well as the message itself, has been shown to make a difference in the outcomes of reaching patients or scheduling appointments.⁴ However, there remains a need for research that identifies the degree to which combinations of patient reminder systems improve outcomes, especially the outcome of on-time immunization, and how these approaches differ by age of child.¹

Following the COVID-19 pandemic shut-down in which thousands of well child appointments were cancelled or delayed, the importance of a systematic outreach process became more critical. The traditional process is non-standardized and the efficacy of the work is both unknown and expensive. Our objective is to determine the effectiveness of varied outreach methods (e.g. automated reminder calls/text messages with or without personalized calls/texts, MyChart messaging) to children age 12-14 months, 4 years old, or 6-17 years old who are due for a WCC visit and don't have one scheduled in the next 45 days on the outcomes of appointment scheduling, appointment completion, and receipt of the MMR vaccination.

2. Design/Method

To achieve our objective, we will conduct a 2×2 factorial randomized controlled trial. Randomization is justified because 1) it is a rigorous approach to answer our question and 2) we do not have the resources or appointment availability to personally contact every patient who is eligible and have them schedule immediately.

Patient Population:

Patients are eligible for inclusion in this study if they are in one of four eligible groups:

12-14 months AND	4 years AND

• doesn't have a well visit scheduled in the next 45 days• have not yet received 12-month immunizations• have English and/or Spanish as preferred language	
• doesn't have a well visit scheduled in the next 45 days• has not had a well child visit in 365 days• have English and/or Spanish as preferred language

6-11 years AND	12-17 years AND

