PPC	Hi, this is [Staff First Name] from PPC. [Pt first name] is due for a check up. I'll call in a day or two to help schedule that appointment or you can walk in today to have your child seen! You can also call [contact], option 1 to schedule.	Hi, this is [First Name] from PPC. I noticed that [Child's First Name] is due for a check up. Can I schedule that for your right now? Alternate script for leaving a voice message: Hi, this is [First Name] from PPC. I noticed that [Child's First Name] is due for a check up. Sorry I missed you. Please call [contact], option 1 to schedule your appointment or walk in today to have your child seen.

*Scripts have been translated into Spanish versions by Interpreter Services

Response variables (outcomes):

- Appointment **was scheduled** within 2 weeks of intervention (Y/N) (date of actual appointment may be greater than 2 weeks from intervention)
- Appointment **was completed** within 8 weeks of intervention (Y/N). Appointment completed within 8 weeks of randomization will be used for group who does not receive any intervention.
- (Primary Outcome) Receipt of MMR by 15 months of age or receipt of 2nd MMR dose by 3 months after randomization (Y/N)
- Receipt of 1st COVID vaccination (ages 12-17 years) within 8 weeks of first intervention (Y/N)
- Family member receipt of COVID vaccination in our health system within 8 weeks of first intervention

Blocking: (controlling for factors that might influence the outcome)

- Age (12-14 months, 4 years)
- Clinic location (PPC, HPC, FPC)

Personal Contacts (12-14 months & 4-year-olds) Trial:

Randomization: Eligible patient will be identified by running a report in the electronic health record (EHR). We will run this report, stratified by clinic location, and randomly assign patients into one of the four groups created by our 2 X 2 design. Groups will receive their assigned intervention in one of four successive weeks with the sequence randomly assigned (see table below).

Replication: We will conduct a total of 3 trials, repeating the randomization procedure every 4 weeks to identify children who become eligible: Weeks 1-4 = trial #1, weeks 5-8 = trial #2, weeks 9-12 = trial #3.

Outreach Methods Study Protocol & SAP

Version 1.1, 1/14/22

	1 automated message sent	2 automated messages sent
0 personal contact attempt	Message sent on Thu (weeks 3, 5, 10)	Message sent on Thu & Fri (weeks 4, 6, 12)

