1 personal contact attempt	Above plus attempt Mon – Fri of following week (weeks 2, 7, 11)	Above plus attempt Mon – Fri of following week (weeks 1, 8, 9)

MyChart and Televox Trials (6-17 years old):

Randomization: Eligible patients will be identified by running a report in the electronic health record (EHR). We will run this report, stratified by clinic location, and randomly assign patients into one of the study groups as described above. Groups will receive their assigned intervention in one of four successive weeks with the sequence randomly assigned (see table below).

We will randomize children who are eligible and implement interventions for each trial : Weeks 1-3 = Televox Trial 12-17yo, Weeks 4-7 = Televox Trial 6-11yo, Weeks 8-10 = MyChart Trial.

MyChart Trial:

	no message	1 MyChart message sent	2 MyChart messages (e.g. Mon and Thurs)
Standard Message	No intervention	Week A	Week B
Tailored Message		Week A	Week B

Televox (6-11yo) Trial:

no message	Low Tailored Message 2 automated standard messages sent (e.g. Thu, Fri) (weeks C, C)	High Tailored Message 2 automated tailored messages sent (e.g. Thu, Fri) (weeks D, D)
-------------------	--	---

Televox (12-17yo) Trial:

no message	Low Tailored Message 2 automated tailored messages sent (e.g. Thu, Fri) (week A)	COVID Tailored Message 2 automated messages sent (e.g. Thu, Fri) (week B)
-------------------	--	---

Of note, automated messages and/or personal contact attempts will not be completed if the parent schedules an appointment after being randomized but before receiving the intervention.

Covariates for logistic regression: (factors that might influence the outcome if not balanced across groups)

1. Child age at the time of randomization (rationale: visits are less frequent for children age 4 years)
2. Parent preference for call vs. text mode of contact (rationale: calls may be more likely to get blocked than texts)
3. Parent with activated MyChart account (Y/N) (rationale: not dependent on calling scheduling center to make appointment)

4. Access to appointment: Number of days to 3rd next available appointment at patient's clinic at time their first automated message is sent
5. Patient receipt of any past immunizations (Y/N) (rationale: vaccine refusing parents will be unlikely to change even if they return for well child check)
6. School-age vs. adolescent patient age (rationale: adolescents less likely to get yearly check-ups)
7. Historical no-show rate

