For the Personal Contact (12-14 mo & 4 years old) trials, we will conduct intent-to-treat analyses using logistic regression models (without adjusting for covariates) for each of our three binary outcomes: completed appointment within 2 weeks, completed appointment within 8 weeks, receipt of MMR by 15 months of age or receipt of 2nd MMR by 3 months after randomization. We will do pair-wise comparison among the 4 groups and adjust p value of each comparison for multiplicity. If participants in the 4 groups differ on potential covariates, we will conduct additional analyses adjusted for these variables.

For the MyChart and Televox Trials (6-17 years old), we will conduct intent-to-treat analyses using logistic regression models (without adjusting for covariates) for each of the binary outcomes: scheduled appointment within 2 weeks, completed appointment within 8 weeks, receipt of 1st dose of COVID vaccination (age 12-17 years) within 8 weeks, family member receipt of COVID vaccination within 8 weeks. We will do pair-wise comparison among the treatment groups and adjust p value of each comparison for multiplicity. If participants differ in potential covariates across treatment groups, we will conduct additional analyses adjusted for these variables. We will explore non-inferiority analysis for comparison the two groups that are expected to have similar appointment scheduled and completion rate in the MyChart trial.

We will also conduct per-protocol analyses according to the interventions actually received by the participants, recognizing that actual intervention received could be different from initial randomized intervention. For example, a parent allocated to group A might schedule an appointment after receiving the automated message and therefore would not receive a personalized contact attempt. In addition, we may explore potential interaction between the two interventions as a secondary analysis. All analysis will be conducted using SAS version 9.4.

Duration

The study will begin upon IRB approval and continue through December 31, 2022. During this time, we will discuss the significance of data, potential future projects and dissemination of results.

Process of Obtaining Consent

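### For 4-year-olds, neither the entry criteria nor the primary outcome rules out a second MMR dose given before randomization, so such a dose can be scored as a success in any arm

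*Combined protocol and SAP*

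**What the plan says.** The protocol's Patient Population table (section 2, Design/Method) sets three conditions for each of the two younger groups. Two are shared: no well visit booked in the next 45 days, and English or Spanish as preferred language. The third differs. Children aged 12-14 months qualify if they "have not yet received 12-month immunizations". Four-year-olds qualify if the child "has not had a well child visit in 365 days". No vaccine condition appears in the 4-year column.

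Under Response variables, the item marked as primary is "Receipt of MMR by 15 months of age or receipt of 2nd MMR dose by 3 months after randomization (Y/N". The second half is the one that applies to 4-year-olds.

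Three other places could have closed the gap and do not:

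- Randomization, Personal Contacts trial: "Eligible patient will be identified by running a report in the electronic health record (EHR". No MMR filter is described.
- Covariates for logistic regression: the only vaccine-history item is "Patient receipt of any past immunizations (Y/N", explained there as a marker of vaccine refusal. It does not identify second-dose status.
- Analysis: "we will conduct intent-to-treat analyses using logistic regression models (without adjusting for covariates". Nothing limits the MMR analysis to children who still need the dose.

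The separate SAP covers only the trial in 12-17-year-olds, so it is silent on this outcome.

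**The concern.** The younger group must lack the vaccine that defines its outcome; the older group need not. The outcome wording does not make up for this. It asks whether the dose was received by a date, whereas the COVID outcome in the same list is tied to a window that opens with the intervention: "Receipt of 1st COVID vaccination (ages 12-17 years) within 8 weeks of first intervention (Y/N".

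A 4-year-old with a recorded second dose therefore carries a fixed result into the trial. On the literal wording the result is Yes. If the team means new doses only, it is No. Either way outreach cannot change it, and the plan does not say which coding applies, so two analysts could report different primary results from the same data.

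The absolute difference is at stake. Power/Sample Size argues that personal contact is costly and that only a large difference would justify it. Children with a fixed result pull the observed difference towards zero on exactly that scale. If they are scored Yes, they also raise the reported vaccination rate in every arm.

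**Working it through.** **Inputs from Power/Sample Size.** Assumed success rates are C 20%, B 35%, A 50% and AB 65%, stated only for MMR by 15 months. Alpha is 0.05 (taken as two-sided), power 80%, 167 per group and 668 in total. There are 712 children currently eligible, not split by age.

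**Assumptions, because the documents give no figure.** Half of each arm is aged 4. A share s of the 4-year-olds already has the second dose, with s = 5%, 10% or 20%. The planning rates also apply to 4-year-olds who still need the dose.

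**Step 1: reproduce the plan's figure.** With unpooled variance, n = (1.960 + 0.842)² × [p1(1−p1) + p2(1−p2)] / (p1−p2)². For A vs B this is 7.849 × (0.2500 + 0.2275) / 0.0225 = 166.6, so 167. The same formula returns all six stated sizes (36, 136, 167, 167, 40, 16). The sample-size arithmetic is not at fault.

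**Step 2: dilution.** The fraction of each arm with a fixed Yes is f = 0.5 × s. Each rate p becomes p(1−f) + f, so every difference is multiplied by (1−f).

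**Step 3: power.** I use the pooled-variance form, which is slightly more conservative than the plan's: power = Φ{[d − 1.960 × √(2p̄(1−p̄)/n)] / √[(p1(1−p1) + p2(1−p2))/n]}. With no affected children it gives 79.5% at n = 167, against 80.1% unpooled. Like the plan's table, it makes no allowance for multiplicity.

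Example, s = 10%: f = 0.05. B = 0.35 × 0.95 + 0.05 = 0.3825, A = 0.50 × 0.95 + 0.05 = 0.525, d = 0.1425, p̄ = 0.45375. Power = Φ[(0.1425 − 1.960 × 0.05448) / 0.05392] = Φ(0.662) = 74.6%.

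**Step 4: remove the affected children.** The rates return to 35% and 50%, and n becomes 167(1−f).

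| Share of 4-year-olds with dose 2 | f | B | A | Difference (points) | Power at 167, as worded | n per arm after exclusion | Power after exclusion |
|---|---|---|---|---|---|---|---|
| 0% | 0 | 35.00% | 50.00% | 15.00 | 79.5% | 167 | 79.5% |
| 5% | 0.025 | 36.63% | 51.25% | 14.63 | 77.1% | 162.8 | 78.4% |
| 10% | 0.05 | 38.25% | 52.50% | 14.25 | 74.6% | 158.7 | 77.4% |
| 20% | 0.10 | 41.50% | 55.00% | 13.50 | 69.6% | 150.3 | 75.1% |

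If these children were coded No instead, each rate would be p(1−f) and the difference would shrink by the same factor.

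**Step 5: the recruitment cushion.** All 712 currently eligible children give 712 / 4 = 178 per arm. At 178 and s = 5%, power as worded is 79.6%; at s = 20% it is 72.4%.

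**The case against.** The case for leaving the plan alone has five parts.

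- **The number may be small.** A 4-year-old with no well visit for 365 days had the last one before the fourth birthday, so an earlier second dose must date from then or have been given outside a well visit. This stands: the rule is a partial proxy. It does not exclude such doses.
- **The item sits under response variables, so a dose after randomization is a natural reading.** Possibly, but the text does not say so. Under that reading a previously vaccinated child becomes a fixed No and still dilutes the difference.
- **Recruitment is expected to exceed 668 comfortably.** This stands in part. Extra children restore power when few are affected, less so at 20%, and they leave the diluted estimate and the undefined coding as they are.
- **The contrasts that isolate personal contact are not threatened.** A vs C and B vs AB keep power above 99.9% even at 20%. This stands; the loss falls on the 15-point contrasts.
- **A vaccinated child overdue for a checkup is a proper subject for the scheduling and completion outcomes.** This stands, and it rules out an entry filter as the main remedy.

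A reader might also infer that a dose given elsewhere always scores Yes. It does so only if the EHR records it. An unrecorded outside dose scores No, and no EHR-based restriction would find that child.

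**Conclusion.** The gap is real and the plan does not close it elsewhere. As worded, a 4-year-old with the second dose already in the EHR can enter and be scored a success in any arm, which dilutes the absolute MMR difference and inflates the reported rate.

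The size is uncertain and probably modest. Under the assumptions above, A vs B power drops by about 2.4, 4.8 or 9.8 points. Restricting the analysis recovers about 1.4, 2.8 or 5.5 of those; the remainder is the cost of a smaller analysis set. These figures depend on an assumed age mix, an assumed share already vaccinated, and planning rates that the protocol does not give for second doses.

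Two stronger conclusions are tempting, and the documents support neither. One is that vaccinated children are in fact being counted as successes: no passage shows that any were enrolled or how their doses are coded. The other is that the comparison is biased: randomization balances children with an already recorded dose across arms in expectation, so the consequence is dilution towards no difference, not a spurious effect.

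**What to change.** Amend the primary outcome and its analysis set, not the entry criteria.

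- Keep all randomized children for the scheduling and completion outcomes.
- For the primary MMR analysis, restrict the 4-year-olds to those with no second MMR dose recorded in the EHR as dated before randomization.
- Define their outcome as a second dose received after randomization and within 3 months.
- Report the number excluded in each arm. This shows how large the problem was and whether the exclusions are balanced, as a baseline characteristic should be.

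The cost is a slightly smaller MMR analysis set: 2.5% to 10% of each arm over the range above. The protocol's consent section says MMR status is already documented in the EHR, so no new data collection is needed. Because the restriction rests on a fact fixed before randomization, the restricted arms remain a randomized comparison, and the change can be made even if enrolment is complete.

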
• doesn't have a well visit scheduled in the next 45 days	
• doesn't have a well visit scheduled in the next 45 days

 • has not had a well child visit > 365 days • have English and/or Spanish as preferred language 	
 • has not had a well child visit in 365 days • have English and/or Spanish as preferred language
---	---

Factors under study (levels):

Personal Contacts (12-14 month & 4-year-olds) Trial:

Number of automated messages sent prior to any personal contact attempts (1 vs. 2)
Number of personal contact attempts made by medical assistant (0 vs. 1)

	1 automated message sent	2 automated messages sent
0 personal contact attempt		
1 personal contact attempt		

MyChart Trial:

Families enrolled in MyChart will be selected and randomized into the following groups:

	no message	1 MyChart message sent	2 MyChart messages (e.g. Mon and Thurs)
Low Tailored Message			
High Tailored Message			

Number of messages (0 vs. 1 vs. 2); Type of messages (low tailored message with name only vs. high tailored message with date of last WCC and age included)

Televox (age 6-11yo) Trial:

Patients will be randomized into the following three groups. Patients with MyChart are excluded:

no message	Low tailored Message 2 automated standard messages sent (e.g. Thu, Fri)	High Tailored Message 2 automated tailored messages sent (e.g. Thu, Fri)
-------------------	---	--

Televox (age 12-17yo) Trial:

Patients will be randomized into the following three groups:

no message	Low Tailored Message 2 automated tailored messages sent (e.g. Thu, Fri)	COVID Tailored Message 2 automated messages sent (e.g. Thu, Fri)
-------------------	---	--

Automated Message: Parents indicate their preferred mode of reminder (e.g. call or text message) when they schedule appointments. Cincinnati Children's uses a HIPAA compliant platform called TeleVox to send automated calls and text reminders to parents according to their preferences which are recorded in the Electronic Health Record (EHR).

Here is the script for **low tailored automated messages** that will be sent via call or text:

Clinic	Message 1*	Message 2*

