8. Community rates of COVID based on 7 day moving average.

Power/Sample Size

Personal Contacts (12-14 month & 4-year-olds) Trial:

We based our hypotheses (see table, below) on a systematic review's pooled estimates of effect size for automated messages and personalized calls finding 37% and 40% of children, respectively, completed immunizations.¹ Because of the significant cost involved in making personal contacts, the minimal difference in outcome that would make it worth the effort is high.

Hypotheses	% of children who receive MMR by 15 months of age	
	1 automated message sent	2 automated messages sent
0 personal attempts	20% ^C	35% ^B
1 personal attempt	50% ^A	65% ^{AB}

We calculated sample size needed per group to detect a difference for each of the contrasts below with alpha of 0.05 and power of 80%.

Contrast	Sample Size per Group
A vs C	36
B vs C	136
A vs. B	167
A vs. AB	167
B vs. AB	40
C vs. AB	16

To fully power the 2 X 2 factorial trial, we estimate needing 167 per group X 4 groups = 668 total subjects. There are currently 712 children eligible for the study. More will become eligible every month so we expect to far exceed the required sample size after 3 replications. If needed, we could increase the number of replications of the trial to reach the targeted sample size. We acknowledge that we are not powered to precisely estimate any interactions between interventions.

MyChart Trial:

In hypothesis testing for 0 message vs. 1 message vs. 2 messages, we will do the testing in a fixed sequence - test 2 messages vs. 0 message first, only if it is significant then test 2 messages vs. 1 message, thus the type I error rate of 0.05 is retained. Since the hypothesis testing of 2 messages vs. 0 message would be considered easier to achieve than the hypothesis testing of 2 messages vs. 1 message, the power analysis for this trial should be based on the design of (standard message vs. tailored message) by (1 message vs. 2 messages). We based our hypotheses (see table, below) on previous work indicating approximately 20% WCC appointment completion on automated text reminders. We anticipate that a tailored message increases the WCC appointment completion rate by another 10%.

Hypotheses		% of children complete WCC within 8 weeks

	No message	1 automated message sent	2 automated messages sent
Standard Message	2%	10% ^C	20% ^B
Tailored Message		20% ^A	30% ^{AB}

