We calculated sample size needed per group to detect a difference for each of the contrasts below with alpha of 0.05 and power of 80%.

Contrast	Sample Size per Group
A vs C	199
B vs C	199
A vs. AB	293
B vs. AB	293
C vs. AB	62

We assume no difference between A vs. B and thus not consider powering the comparison between these two groups, but we will explore non-inferiority analysis for this comparison in data analysis. To fully power the above contrasts, we estimate needing 293 per group X 4 groups = 1172 subjects. Adding 293 in the zero message group, we would need a total of 1465 subjects. There are currently 1000 children eligible for the study. More will become eligible every month so we expect to exceed the required sample size after 2 replications. If needed, we could increase the number of replications of this trial to reach the targeted sample size. We acknowledge that we are not powered to precisely estimate any interactions between interventions.

Televox (6-11yo) Trial:

We calculated sample size based on the following hypotheses:

% of children complete WCC within 8 weeks		
no message	2 Low Tailored Messages	2 High Tailored Messages
2%	20%	30%

With alpha of 0.05 and power of 80%, to fully power the contrasts between the above groups, we need 293 per group X 3 groups=879 subjects. Currently there are 2500 kids eligible, so we expect to reach the targeted sample size.

Televox (12-17yo) Trial:

We calculated sample size based on the following hypotheses:

% of children complete WCC within 8 weeks		
no message	2 Low Tailored Messages	2 COVID Tailored Messages
2%	30%	40%

With alpha of 0.05 and power of 80%, to fully power the contrasts between the above groups, we need 356 per group X 3 groups=1068 subjects. Currently there are 1100 kids eligible, so we expect to reach the targeted sample size.

Analysis

We will conduct descriptive analyses to characterize the participants in terms of demographics and other potential covariates in consideration (child age group, parent's preference for call vs. text mode of contact, whether parent

Outreach Methods Study Protocol & SAP

Version 1.1, 1/14/22

pg. 9

had activated MyChart account, access to appointment, whether patient receipt of any past immunizations, historic no show rate, and community rates of COVID). We will use chi square tests to examine whether participants in the 4 groups are similar in these characteristics.

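### MyChart trial: the protocol names both families and patients as the unit randomized, and if it is families, the planned child-level logistic model understates the standard errors

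*Combined protocol and SAP*

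**What the plan says.** The protocol describes the unit of randomization for the MyChart trial in two places.

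- Section 2, Factors under study, MyChart Trial: "Families enrolled in MyChart will be selected and randomized into the following groups". In the same list, both Televox trials are said to randomize patients. Only MyChart refers to families.
- MyChart and Televox Trials (6-17 years old), Randomization: the investigators will run an EHR report and "randomly assign patients into one of the study groups as described above". The next paragraph adds: "We will randomize children who are eligible and implement interventions for each trial".

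The sizing and the analysis are at child level.

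- Power/Sample Size, MyChart Trial: the hypothesis table gives the percentage "of children complete WCC within 8 weeks". The requirement is 293 per group, 1172 over four message groups and 1465 with the no-message group. The pool is also counted in children: "There are currently 1000 children eligible for the study".
- Analysis: "we will conduct intent-to-treat analyses using logistic regression models (without adjusting for covariates) for each of the binary outcomes".

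The protocol has no rule for siblings, no limit of one child per family, and no cluster term, robust variance or design effect. The separate SAP covers only the text and telephone trial in 12-17-year-olds, so it does not settle the question.

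**The concern.** The two statements describe different trials. If families are randomized, all eligible children in a family receive the same assignment, and one parent usually decides whether to book. Sibling outcomes are then likely to be positively correlated within an arm. An ordinary logistic model on children ignores this, so its standard errors are too small and its confidence intervals too narrow. 293 children also carry less information than 293 independent subjects. The trial covers ages 6 to 17, so a family can have more than one eligible child, and the covariate list records the MyChart account as the parent's. If children are randomized one by one, this mechanism does not operate in the same form. As the protocol stands, a reader cannot tell which case applies, and so cannot tell whether the planned model is valid.

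**Working it through.** **Inputs from the protocol.** Two-sided alpha 0.05 (sidedness is not stated, but two-sided reproduces the figures), power 80%, and rates of 10%, 20% and 30%. The stated sizes per group are 199 (10% vs 20%), 293 (20% vs 30%) and 62 (10% vs 30%).

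**Inputs assumed.** Eligible children per family, m, and within-family correlation, ICC. The documents give neither. The range used is m = 1.1 to 1.5 and ICC = 0.3 to 0.8.

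**Step 1: reproduce the plan.** For two independent proportions with pooled variance under the null and no continuity correction:

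n = [1.96·√(2p̄(1−p̄)) + 0.842·√(p₁(1−p₁)+p₂(1−p₂))]² / (p₂−p₁)²

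- 20% vs 30%: 293.15 (stated 293)
- 10% vs 20%: 198.96 (stated 199)
- 10% vs 30%: 61.6 (stated 62)

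Power at 293 is Φ[(0.1·√293 − 1.96·√0.375)/√0.37] = Φ(0.841) = 79.98%. The plan's figures are therefore those for independent children with no design effect, and there is no margin above 80%.

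**Step 2: consequence if families are randomized.** With equal family sizes:

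- design effect DE = 1 + (m−1)·ICC
- effective n = 293/DE
- true size of an unadjusted nominal 0.05 test that ignores clustering = 2·[1 − Φ(1.96/√DE)]
- power of a correctly clustered test: the Step 1 power formula with 293/DE in place of 293
- rejection probability of the uncorrected test at 20% vs 30%: Φ(0.841/√DE), because the critical value is unchanged while the true standard error is larger by √DE

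| m | ICC | DE | Effective n | True size, uncorrected | Power, clustered test | Rejection rate, uncorrected |
|---|---|---|---|---|---|---|
| 1.0 | any | 1.00 | 293 | 5.0% | 80.0% | 80.0% |
| 1.1 | 0.3 | 1.03 | 284 | 5.3% | 78.8% | 79.6% |
| 1.2 | 0.5 | 1.10 | 266 | 6.2% | 76.1% | 78.9% |
| 1.5 | 0.5 | 1.25 | 234 | 8.0% | 70.7% | 77.4% |
| 1.5 | 0.8 | 1.40 | 209 | 9.8% | 65.7% | 76.1% |

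The last two columns describe different tests. The true size belongs with the uncorrected test. The clustered power is what remains once the size is restored to 5%.

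**Step 3: unequal families.** Here DE = 1 + (E[m²]/E[m] − 1)·ICC. Suppose 80%, 18% and 2% of families have one, two and three eligible children. Then E[m] = 1.22, E[m²] = 0.80 + 0.72 + 0.18 = 1.70 and the ratio is 1.393. At ICC 0.5, DE = 1.20, the true size is 7.3% and clustered power is 72.5%. The equal-size formula is therefore the favourable case for a given mean.

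**Step 4: restoring 80% power with all children kept.** The requirement is 293 × DE children per arm: 302 at DE 1.03 (5 × 302 = 1510 in total) and 411 at DE 1.40 (5 × 411 = 2055).

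**The case against.** The strongest reply is that the child is the intended unit and that the word families is loose drafting. The Randomization paragraph, where the procedure is set out, refers to patients and children. Eligibility, the hypothesis table and the pool are all per child, and the tailored text carries the child's own details. The protocol also speaks of contacting families in the personal-contact trial, which assigns patients. Most of this stands: the weight of the text favours the child. It does not remove the contradiction. The Randomization paragraph refers back to the groups described earlier, and that is where the families sentence sits. The neighbouring Televox entries use patients, so the difference in wording cannot be dismissed as a uniform habit.

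Three stronger readings are tempting, and the documents do not support them.

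- A reader might infer that the protocol contains a definite unit-of-analysis error that inflates type I error in every MyChart contrast. The text establishes only an ambiguity. The inflation follows if families are randomized, siblings are enrolled together and their outcomes are positively correlated.
- A reader might take 66% as the power of the analysis as planned. It is the power of a corrected test at the unfavourable end of the assumed range. The uncorrected test rejects about 76% of the time there, at an inflated size.
- A reader might conclude that 293 must always count households. That is right only for one index child per family. With all children kept at m = 1.2 and ICC 0.5, the need is 293 × 1.10/1.2, or about 269 households.

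The size figures are also for a single unadjusted test. The plan uses a fixed sequence for the number of messages and multiplicity-adjusted pairwise p values, and those procedures were not evaluated here.

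**Conclusion.** The point holds conditionally. The contradiction over the unit is plain in the text, and both the sizing and the model assume independent children. If the family is the unit, the naive standard errors are too small by a factor √DE, which is 1.01 to 1.18 over the assumed range. The effect runs from negligible (m = 1.1, ICC 0.3: size 5.3%, clustered power 78.8%) to material (m = 1.5, ICC 0.8: size 9.8%, clustered power 65.7%), and it is nil with one eligible child per family. Where in that range the trial would fall cannot be determined from the documents. If children are the unit, this variance argument does not apply in that form and only a wording correction remains. The point concerns the MyChart trial alone.

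**What to change.** Make the MyChart entry under Factors under study and the Randomization paragraph name the same unit.

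- **If it is the child:** correct the families sentence. Nothing further follows from this point.
- **If it is the family, option 1:** prespecify one index child per family, chosen by a rule fixed before randomization, and analyse only that child. Here 293 per arm counts families.
- **If it is the family, option 2:** keep all eligible children and fit the logistic model with household as the cluster (GEE with robust variance, available in SAS). State an assumed design effect, and say that 293 children per arm carry the information of 293/DE independent subjects. To hold 80% power, enrol 293 × DE children per arm.

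The cost is small: a sentence or two of protocol text, one model option and a household identifier. The family-member COVID vaccination outcome, listed in the Analysis section for these trials, already calls for some family linkage. The downside is slightly wider intervals and a less favourable stated power, or a larger enrolment if 80% is to be kept.
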